Study Title: Improving Influenza Vaccination Delivery Across a Health System by the Electronic Health Records Patient Portal RCT 5

Initial IRB Approval: 12/20/2017

RCT 5 IRB Approval: 8/18/2022

Clinical Trials Registration: NCT05525494

Protocol

Brief Summary:

This trial is taking place in Los Angeles, CA among patients from primary care practices within the UCLA Health System.

Despite the Advisory Committee on Immunization Practices (ACIP) recommendation in 2010 that all people above 6 months of age should receive an annual flu vaccine, vaccination rates remain low. The investigators plan to assess the effectiveness of text and portal reminder/recall messages with direct appointment scheduling (pre-appointment, and no pre-appointment) encouraging influenza vaccinations sent to patient portal users, as well as the effectiveness of tailored portal reminder/recall messages based on responses from pre-commitment prompt asking which time and which place they plan to receive their influenza vaccine using a 2 x 2 nested factorial design.

Methods and Procedures

We propose a three-arm randomized controlled trial, and a 2 x 2 nested factorial design within the intervention arms. Patients are randomized within UCLA primary care practices into 1) receiving text based R/R messages with direct scheduling link, 2) portal-based R/R messages with direct scheduling link, or 3) the control group. Patients randomized to the intervention arms will receive reminders if they are due for influenza vaccine.

Nested within the portal reminder arm, we will have two additional components for which patients will be randomized separately: 1) A pre-commitment prompt, asking patients which time (September, October, November or December) and which place (UCLA, pharmacy, workplace or school, or other) they plan to get their Influenza vaccine with tailored monthly messages based on responses (pre-commitment message with tailored recall messages with direct scheduling vs. standard (“fixed”) portal reminders with direct scheduling); 2) A pre-appointment reminder encouraging patients to ask for their influenza vaccine at their upcoming appointment (pre-appointment reminder encouraging influenza vaccination vs. standard pre-appointment reminder not mentioning influenza vaccination)

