Nested within the text message reminder arm, we will have one additional component for which patients will be randomized separately: 1) A pre-appointment reminder encouraging patients to ask for their influenza vaccine at their upcoming appointment (pre-appointment reminder encouraging influenza vaccination vs. standard pre-appointment reminder not mentioning influenza vaccination).

Spacing of R/R messages: The pre-commitment prompt will be sent in September, direct appointment scheduling and no direct appointment scheduling reminders will be sent one time per month until record of vaccine receipt appears in the patient EHR in October, November, and December. The pre-appointment reminders will be sent 2-4 days in advance of scheduled visits.

Languages: messages will be in English.

Health Literacy: We will use plain language <7th grade reading level per Flesch-Kincaid analysis.

Eligibility: Our EHR will identify subjects who are eligible for either 1 or 2 influenza vaccinations based on ACIP algorithms (2 are recommended for children <9 years who have not had prior vaccination).

Inclusion criteria

Inclusion criteria will involve-- all UCLA primary care patients over 4 months of age who have made at least 1 visit to the practice within the prior 3 years and who have signed up for MyUCLAhealth (UCLA's portal) and have used the portal at least once within 12 months, from these patients, index patients per household will be randomly selected.

- a. Active patient: We selected >1 visit in 3y based on our prior studies and the literature to focus the intervention on active patients; practices do not have a good mechanism to inactivate patients.
- b. Focusing on Portal Users: We can only send portal R/R messages to patients who have signed up for the portal. Since some patients sign up for the portal but never use it we will restrict our inclusion criteria to patients who used the portal within 12m (75% of UCLA patients). This standard has been applied before. We will assess intervention effects for the included population, and also for the entire practice, since the impact of the intervention reflects the extent of portal penetration.

Exclusion criteria

Patients will be excluded if they are not a patient at one of the 67 primary care practices within UCLA's Health System, and/or if they do not meet the above specified requirements for being an active patient or portal user.

Main Outcomes and Measures

Primary Measures:

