
Active Comparator: Portal Pre-Commitment Prompt, Tailored R/R Messages w/ Direct Scheduling + Pre-Appointment Reminders
 
Participants in this arm will receive a pre-commitment prompt message by portal in September. Tailored R/R messages will be sent monthly by portal based on time and place selected by patients (up to 3). R/R message will be sent with a Direct Appointment Scheduling link and instructions to make a flu vaccine appointment.
 
Participants will receive a Pre-Appointment Reminder advising them to ask their doctor for the flu vaccine at their upcoming appointment via portal when they schedule a visit during the study period.
	
Behavioral: Portal Pre-Commitment Prompt with Tailored R/R Messages with Direct Appointment Schedule Link
 
Participants in this arm will receive a pre-commitment prompt message by portal in September. Tailored R/R messages will be sent monthly by portal based on time and place selected by patients (up to 3). R/R message will be sent with a Direct Appointment Scheduling link and instructions to make a flu vaccine appointment.
 
Behavioral: Portal Pre-Appointment Reminder
 
Participants will receive a Pre-Appointment Reminder advising them to ask their doctor for the flu vaccine at their upcoming appointment

	via portal when they schedule a visit during the study period.
Active Comparator: Portal Pre-Commitment Prompt with Tailored R/R Messages with Direct Appointment Schedule Link Participants in this arm will receive a pre-commitment prompt message by portal in September. Tailored R/R messages will be sent monthly based on time and place selected by patients (up to 3). R/R message will be sent with a Direct Appointment Scheduling link and instructions to make a flu vaccine appointment.	Behavioral: Portal Pre-Commitment Prompt with Tailored R/R Messages with Direct Appointment Schedule Link Participants in this arm will receive a pre-commitment prompt message by portal in September. Tailored R/R messages will be sent monthly by portal based on time and place selected by patients (up to 3). R/R message will be sent with a Direct Appointment Scheduling link and instructions to make a flu vaccine appointment.

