Active Comparator: Portal Fixed R/R Messages with Direct Appointment Schedule Link + Portal Pre-Appointment Reminder Participants in this arm will receive up to 3 R/R messages by portal. R/R message will be sent with a Direct Appointment Scheduling link and instructions to make a flu vaccine appointment. Participants will receive a Pre-Appointment Reminder advising them to ask their doctor for the flu vaccine at their upcoming appointment via portal when they schedule a visit during the study period.	Behavioral: Portal Fixed R/R Messages with Direct Appointment Schedule Link Participants in this arm will receive up to 3 R/R messages by portal. R/R message will be sent with a Direct Appointment Scheduling link and instructions to make a flu vaccine appointment. Behavioral: Portal Pre-Appointment Reminder Participants will receive a Pre-Appointment Reminder advising them to ask their doctor for the flu vaccine at their upcoming appointment via portal when they schedule a visit during the study period.
Active Comparator: Portal Fixed R/R Messages with Direct Appointment Schedule Link Participants in this arm will receive up to 3 R/R messages by portal. R/R message will be sent with a Direct Appointment Scheduling link and instructions to make a flu vaccine appointment.	Behavioral: Portal Fixed R/R Messages with Direct Appointment Schedule Link Participants in this arm will receive up to 3 R/R messages by portal. R/R message will be sent with a Direct Appointment Scheduling link and instructions to make a flu vaccine appointment.
No Intervention: No R/R Message or Pre-Appointment Reminder	

Participants do not receive any flu vaccine R/R message or Pre-Appointment Reminder advising them to ask their doctor for the flu vaccine at their upcoming appointment during the specified flu season.

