Study Title: Improving Influenza Vaccination Delivery Across a Health System by the Electronic Health Records Patient Portal RCT 5

Initial IRB Approval: 12/20/2017

RCT 5 IRB Approval: 8/18/2022

Clinical Trials Registration: NCT05525494

Statistical Analysis

Primary Analysis

We hypothesize that patients receiving text R/R messages will have higher influenza vaccination rates than portal R/R messages and no R/R; we hypothesize patients receiving the pre-commitment prompt will have higher influenza vaccination rates than standard portal R/R messages and no R/R; and we hypothesize that patients receiving pre-commitment prompts will have higher influenza vaccination rates than no prompts. Primary outcomes (patient receipt of flu vaccine) are binary; our main explanatory variable will be an indicator for the receipt of any portal-based R/R or prompt.

The primary outcome will be the patient's end of flu season vaccination status. Intervention effects will be assessed using mixed effects log-binomial models. Models will contain terms for messaging modality (text v. portal v. none), pre-appointment reminders (sent v. not sent), and, for the portal intervention arm, a pre-commitment prompt (sent v. not sent; this is not included in the text-based arm). Models will adjust for patient characteristics, including age, sex, race/ethnicity, primary language, primary insurer, and prior year vaccination status. Practice random effects will be used to account for clustering of patients by primary care practice. Primary assessment will involve performing model contrasts, and a significance level of 0.017 will be used (3-fold Bonferroni correction of 0.05). To evaluate the combined effect of interventions, we will fit a second model introducing interactions between messaging modality and the other two intervention terms. These analyses will use a significance level of 0.05. Intervention effects will be summarized in terms of risk ratios and 95% confidence intervals.

For RCT #5, individual patients who opt out of text messages will be excluded from the final analysis. In addition, if practices do not send pre-appointment reminders via text, for the pre-appointment analysis the patients from the practice will be excluded from the final analysis. In addition, non-portal users will be excluded from the final analyses.

Secondary Analysis

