Secondary analyses will include evaluation of effect modification by patient characteristics. Effect heterogeneity will be evaluated by introducing interaction terms into the primary model specification. All secondary analyses will use a significance level of 0.05. All analyses will be performed using SAS v. 9.4 (SAS Institute Inc., Cary, NC).

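### The combined-effect model adds a modality by prompt term that cannot be estimated and leaves out the prompt by reminder interaction that can

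*SAP*

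**What the plan says.** The SAP (Primary Analysis, second paragraph) fits a main-effects model with three intervention terms: messaging modality (text, portal, none), pre-appointment reminder, and "a pre-commitment prompt (sent v. not sent; this is not included in the text-based arm"). It then gives a second model its purpose, "To evaluate the combined effect of interventions", and its content: "we will fit a second model introducing interactions between messaging modality and the other two intervention terms". Results from that model are tested at 0.05.

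The Protocol (Methods and Procedures) sets out the nesting:

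- Portal: "Nested within the portal reminder arm, we will have two additional components for which patients will be randomized separately". These are the prompt and the reminder, and the arm table lists a cell with both: "Portal Pre-Commitment Prompt, Tailored R/R Messages w/ Direct Scheduling + Pre-Appointment Reminders".
- Text: "Nested within the text message reminder arm, we will have one additional component for which patients will be randomized separately". This is the reminder only.
- Control: "Participants do not receive any flu vaccine R/R message or Pre-Appointment Reminder". The prompt is not given there either.

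The only other interactions planned are in the SAP's Secondary Analysis: "Secondary analyses will include evaluation of effect modification by patient characteristics".

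**The concern.** An interaction between modality and prompt asks whether the prompt works differently by modality. With the prompt confined to one modality, the data hold no information on that. The two add-ons, by contrast, are separately randomised within the portal arm, so whether one changes the effect of the other can be estimated directly. The SAP names the first and omits the second.

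Without a prompt by reminder term, both models force the two risk ratios to multiply. A health system choosing between one add-on and both needs to know whether the second still helps once the first is in place. That is part of the combined effect the second model is meant to evaluate, and no planned analysis reports it.

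**Working it through.** **Inputs.** The Protocol's arm table gives seven cells: control; text without and with reminder; portal with neither add-on, reminder only, prompt only, and both. Let T and G indicate text and portal, R the reminder and P the prompt. P is taken as 0 outside portal; the SAP does not state the coding. The documents give no degrees of freedom, vaccination rates or cell sizes for this model, so there is no stated figure to reproduce.

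**Step 1: what each term adds.** The degrees of freedom a term contributes are the increase in rank of the design matrix over the seven cells.

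| Model | Columns | Rank |
|---|---|---|
| Main effects: 1, T, G, R, P | 5 | 5 |
| + modality × prompt (TP, GP) | 7 | 5 |
| + modality × reminder (TR, GR) | 7 | 6 |
| SAP second model (both pairs) | 9 | 6 |
| Main effects + TR + PR | 7 | 7 |

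TP is zero in every cell and GP equals P, so modality × prompt adds 5 − 5 = 0. Modality × reminder adds 6 − 5 = 1 (text v. portal), because control has no reminder. Seven cells minus rank 6 leaves one contrast unmodelled, and adding PR supplies it. Fitted values with and without modality × prompt are identical, so the empty term does no numerical harm.

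**Step 2: effect of the omission.** Let g be the true ratio of risk ratios, g = RR(both) / [RR(prompt alone) × RR(reminder alone)], each against fixed portal messages. With equal portal cells, least squares on the log scale without PR gives:

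- fitted portal-fixed and fitted both-add-ons cell: true log value − (ln g)/4;
- fitted prompt or reminder RR v. portal-fixed: log RR alone + (ln g)/2;
- both v. portal-fixed: unchanged, because the two shifts cancel.

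Two illustrations follow. The risk ratios are assumed, and portal-fixed is set equal to control.

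| | Synergy: true | Synergy: second model | Substitution: true | Substitution: second model |
|---|---|---|---|---|
| Prompt v. portal-fixed | 1.01 | 1.020 | 1.03 | 1.015 |
| Reminder v. portal-fixed | 1.01 | 1.020 | 1.03 | 1.015 |
| Both v. portal-fixed | 1.04 | 1.040 | 1.03 | 1.030 |
| Portal-fixed v. control | 1.00 | 0.995 | 1.00 | 1.007 |
| Both v. control | 1.04 | 1.035 | 1.03 | 1.038 |

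For synergy, g = 1.04/1.01² = 1.0195, ln g = 0.0193 and (ln g)/4 = 0.0048. For substitution, g = 1.03/1.03² = 0.9709, ln g = −0.0296 and (ln g)/4 = −0.0074. The model with PR returns the true column in both cases. Log-binomial maximum likelihood without a random effect, at baseline rates of 40% to 60%, gives the synergy results to within about 0.001.

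Over a wider assumed range of g, the fitted both v. control ratio is off by a factor g^(−1/4): 1.027 at g = 0.90, 1.013 at 0.95, 0.988 at 1.05 and 0.976 at 1.10.

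**Step 3: precision of the added term.** With n patients per portal cell and vaccination rate p, ignoring clustering and covariates, SE(ln g) = √[4(1−p)/(pn)]. The SE of a component effect averaged over the other is half of that. Take p = 0.5 (assumed). The ratio detectable with 80% power at two-sided 0.05 is exp(2.80 × SE).

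| n per cell (assumed) | SE(ln g) | Detectable interaction ratio | Detectable averaged RR |
|---|---|---|---|
| 5,000 | 0.0283 | 1.08 | 1.04 |
| 20,000 | 0.0141 | 1.04 | 1.02 |

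**The case against.** The strongest reply has four parts.

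- **The empty term is harmless and the missing one was never promised.** Software drops the aliased columns. None of the SAP's hypotheses concerns synergy between prompt and reminder, and analysing a factorial on main effects alone is a common, defensible choice. The second model still gives a correct ratio for both add-ons against fixed portal messages. All of this is true. But the SAP does not stop at main effects. It commits to an interaction model for combined effects and then specifies one interaction that cannot be estimated while passing over one that can.
- **A three-way term may have been meant.** It would alias to prompt by reminder and restore rank 7. The wording names pairwise interactions with modality, so if a three-way term was intended the SAP should say so.
- **The distortion is small.** At the assumed rate and cell sizes, with control the same size as a portal cell, the SE of portal-fixed v. control in the second model is √(1.75/n), or 0.019 to 0.009. The shifts of 0.005 and 0.007 are below one SE. This stands: no conclusion is shown to flip. In the illustrations, though, the shifts are not small beside the component effects themselves.
- **The interaction would rarely be detected.** By the SE above, power is about 10% to 28% for the synergy case and 18% to 55% for substitution. Reminders also reach only patients who book a visit, which dilutes an as-randomised interaction. This stands too, and is why the added term should be reported as an estimate with its interval. A non-significant result would not exclude either pattern.

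**Conclusion.** The concern holds. That modality by prompt has no degrees of freedom, and that the one missing contrast is prompt by reminder, follows from the seven arms alone. It rests only on the pairwise reading of the SAP sentence and on the prompt being coded 0 outside portal. If it were coded as missing, text and control patients would drop out of the model.

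The consequence is limited. The second model is not void, and it recovers each component's averaged effect and the effect of both over fixed portal messages. It cannot give either component's effect alone or the interaction. If an interaction exists, portal-fixed v. control and both v. control move by a factor g^(−1/4), about 0.5% to 0.7% in the two illustrations. Those sizes depend on assumed risk ratios and equal cells. The point should be corrected because the model, as specified, does not fully answer its own question.

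**What to change.** Replace the sentence that defines the second model with: *The second model adds (i) modality × pre-appointment reminder (text v. portal) and (ii) pre-commitment prompt × pre-appointment reminder within the portal arm, with the prompt coded 0 outside that arm.* Delete modality × prompt.

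Report the prompt × reminder ratio of risk ratios with its 95% CI, together with each component's effect averaged over the other. If cell-by-cell risk ratios are shown (six v. control and three v. portal-fixed), label them descriptive, because those nine comparisons have no multiplicity control.

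The cost is one SAP sentence and no new data. With equal portal cells the averaged component effects keep their precision. The SAP should acknowledge that the interaction's standard error is twice theirs, so a small interaction will be bounded by its interval rather than reliably detected.

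### Primary contrasts are judged at 0.017, but the only stated interval level is 95%, with no note that these intervals are unadjusted

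*SAP*

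**What the plan says.** The relevant text is in the SAP. Under Primary Analysis, the model is set by "Intervention effects will be assessed using mixed effects log-binomial models". The decision rule for the main comparisons is "Primary assessment will involve performing model contrasts, and a significance level of 0.017 will be used", which the SAP explains as 0.05 with a 3-fold Bonferroni correction.

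The same paragraph then introduces a second model with interactions between messaging modality and the other two intervention terms. For that model it says "These analyses will use a significance level of 0.05". The paragraph closes with "Intervention effects will be summarized in terms of risk ratios and 95% confidence intervals".

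Under Secondary Analysis the threshold is again the conventional one: "All secondary analyses will use a significance level of 0.05".

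Neither document gives another confidence level, an adjusted or simultaneous interval, or a rule for reading a 95% interval against the 0.017 threshold. The SAP does not say whether tests are one-sided or two-sided.

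**The concern.** A 95% interval corresponds to a two-sided test at 0.05. For the interaction model and the secondary analyses, both tested at 0.05, that is the right match. For the primary contrasts it is not: the test has a stricter threshold than the interval printed beside it. A primary risk ratio can therefore appear with an interval that excludes 1 and a formal conclusion of no significant difference.

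What is at stake is how the primary results are read. Many readers take the answer from the interval rather than from a threshold in the methods section. A borderline contrast would offer two readings, and the SAP does not say in advance how the interval is to be read beside the test.

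**Working it through.** **Inputs.** From the SAP, Primary Analysis: overall level 0.05; three-fold correction; per-contrast level 0.017; 95% intervals; risk ratio as effect measure, so the null value is 1. Assumed: a normally distributed test statistic on the log risk ratio scale and two-sided tests. The one-sided case is checked in step 6. Neither document gives a sample size or power figure, so the power values below are illustrations.

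**1. The plan's own figure.** 0.05 / 3 = 0.01667, which rounds to 0.017. The stated level reproduces.

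**2. Critical values (two-sided).**

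| Rule | Level | Critical abs(z) |
|---|---|---|
| 95% interval excludes 1 | 0.05 | 1.960 |
| Primary test, as stated | 0.017 | 2.387 |
| Primary test, unrounded | 0.05/3 | 2.394 |

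The interval that matches the primary test has level 1 − 0.017 = 98.3% (1 − 0.05/3 = 98.33%). On the log scale it is wider than the 95% interval by 2.387 / 1.960 = 1.218, or 2.394 / 1.960 = 1.221 with the unrounded level: about 22% either way.

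**3. Where test and interval disagree.** They disagree when 1.960 < abs(z) < 2.387, that is, when 0.017 < p < 0.05.

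**4. Illustration (assumed values).** Take a risk ratio of 1.03 with z = 2.20. The standard error is ln(1.03) / 2.20 = 0.01344, and p = 0.028.
- 95% interval: exp(0.02956 ± 1.960 × 0.01344) = 1.003 to 1.057, which excludes 1.
- 98.3% interval: exp(0.02956 ± 2.387 × 0.01344) = 0.997 to 1.064, which includes 1.

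The planned test would call this contrast non-significant.

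**5. How often, per contrast.** With true effect δ in standard errors, and ignoring the negligible opposite tail when δ is large, P(disagree) = Φ(2.387 − δ) − Φ(1.960 − δ).

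| Situation | δ | P(disagree) |
|---|---|---|
| Null (both tails) | 0 | 0.05 − 0.017 = 3.3% |
| 50% power at 0.017 | 2.387 | 0.500 − 0.335 = 16.5% |
| 80% power at 0.017 | 2.387 + 0.842 = 3.228 | 0.200 − 0.102 = 9.8% |

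The maximum is about 16.9%, at δ near 2.17. With 80% power, 20% of contrasts miss 0.017, and 9.8 / 20 = 49% of those would still show a 95% interval excluding 1. Using 2.394 instead of 2.387 gives 16.8% and 9.9% for the last two rows, so the rounding is immaterial.

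**6. If 0.017 is one-sided.** The critical value is 2.120, still above 1.960. For effects in the hypothesised direction, the conflict then narrows to 1.960 < z < 2.120, a two-sided p between 2 × 0.017 = 0.034 and 0.05. The probabilities in step 5 and the 22% in step 2 apply only to the two-sided case.

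**The case against.** The strongest reply is that nothing in the plan is wrong. The 0.017 rule decides the primary contrasts, and the interval sentence says only how effects are summarised. A 95% interval has its own 95% coverage for each contrast, and unadjusted intervals beside an adjusted test are a coherent choice. The SAP does not say that significance is read from the interval, and it claims no simultaneous coverage. This stands as far as the test goes. What it leaves open is labelling: the choice is acceptable when declared, and this SAP does not declare it.

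A second reply is that the 95% sentence directly follows the interaction model, tested at 0.05, and may refer only to that. The reading is possible but less natural. The sentence speaks of intervention effects without restriction, the same term that introduces the models earlier in the paragraph. On the narrow reading the primary contrasts would have no interval level at all, and the SAP would still need a sentence.

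Third, sidedness is not stated and the hypotheses are directional, for example "We hypothesize that patients receiving text R/R messages will have higher influenza vaccination rates than portal R/R messages and no R/R". That is fair; the conflict is narrower if the 0.017 is one-sided, but it does not vanish.

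Two stronger inferences are tempting and should be resisted. A reader might infer that the intervals undo the Bonferroni correction, since treating three 95% intervals as tests would allow a family-wise error of up to 3 × 0.05 = 15%. The documents do not support this, because the SAP does not replace its test with the intervals. A reader might also compute joint coverage of 0.95³ = 85.7% for three intervals. That assumes independent contrasts, whereas these come from one model and the text comparisons with portal and with no messages share an arm. Nor does the SAP list which three contrasts form the family.

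**Conclusion.** The point holds as a minor reporting inconsistency. On the natural reading of the SAP, the primary contrasts are decided at 0.017 and displayed with 95% intervals that are not identified as unadjusted. With two-sided tests, any contrast with 0.017 < p < 0.05 would carry a non-significant result and an interval excluding 1. That happens with probability 3.3% per contrast under the null and about 10% to 17% when power at 0.017 is between 80% and 50%.

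The validity of the primary test, its family-wise error and the per-contrast coverage of the 95% intervals are not in question. Whether readers would be misled depends on how they read the results; it is a risk, not a certainty. The sizes rest on a normal approximation, two-sided testing and illustrative power.

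**What to change.** In the SAP's Primary Analysis section:

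- Report 98.3% intervals (1 − 0.05/3) for the primary contrasts.
- Show 95% intervals in a second column, labelled as not adjusted for multiplicity.
- State that significance of the primary contrasts is judged only at 0.017, and whether that test is one-sided or two-sided. The 98.3% level is the match for a two-sided test. Using 0.05/3 unrounded for both test and interval avoids a trivial mismatch between 0.0167 and 0.017.
- Keep 95% intervals for the interaction model and the secondary analyses, which are tested at 0.05.

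A lighter alternative is to keep 95% intervals throughout and add one sentence saying that they are unadjusted and that the primary contrasts are judged only at 0.017. This removes the ambiguity but still leaves error bars that do not show the decision rule.

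The cost is a sentence or two in the SAP and a changed confidence level in the SAS code. Design, data and sample size are untouched. The visible downside is that the primary intervals are about 22% wider on the log scale.

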- 1) Receipt of >1 influenza vaccine among index patients between 9/1/2022-4/1/2023 as documented in the EHR which is supplemented electronically by the health system with influenza vaccination data from external sources (e.g., pharmacies) and claims data.
- 2) Receipt of >1 influenza vaccine among pediatric index patients between 9/1/2022-4/1/2023 as documented in the EHR which is supplemented electronically by the health system with influenza vaccination data from external sources (e.g., pharmacies) and claims data.

Secondary Measures: Receipt of annual influenza vaccine between 9/1/2022-4/1/2023 among all included patients in identified households.

Study Arm	Intervention/Treatment

Active Comparator: Text Fixed R/R Messages with Direct Appointment Schedule Link + Text Pre-Appointment Reminders
 
Participants in this arm will receive up to 3 R/R messages by text. R/R message will be sent with a Direct Appointment Scheduling link and instructions to make a flu vaccine appointment. Participants will receive a Pre-Appointment Reminder via text when they schedule a visit during the study period.
	
Behavioral: Text Fixed R/R Messages with Direct Appointment Schedule Link
 
Participants in this arm will receive up to 3 R/R messages by text. R/R message will be sent with a Direct Appointment Scheduling link and instructions to make a flu vaccine appointment.
 
Behavioral: Text Pre-Appointment Reminder
 
Participants will receive a Pre-Appointment Reminder via text when they schedule a visit during the study period.

Active Comparator: Text Fixed R/R Messages with Direct Appointment Schedule Link
 
Participants in this arm will receive up to 3 R/R messages by text. R/R message will be sent with a Direct Appointment Scheduling link and instructions to make a flu vaccine appointment.
	
Behavioral: Text Fixed R/R Messages with Direct Appointment Schedule Link
 
Participants in this arm will receive up to 3 R/R messages by text. R/R message will be sent with a Direct Appointment Scheduling link and instructions to make a flu vaccine appointment.

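### The exclusion of text opt-outs is not limited to opt-outs recorded before randomisation in all arms, so it can bias text v. portal and text v. none

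*SAP*

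**What the plan says.** The third paragraph of the SAP's Primary Analysis section says that "individual patients who opt out of text messages will be excluded from the final analysis". It gives no date relative to randomisation, no arm and no source for the opt-out record. The same paragraph says that "non-portal users will be excluded from the final analyses", and it drops practices that do not send pre-appointment reminders by text, the latter for the pre-appointment analysis only.

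The protocol does not mention opting out. Its criteria concern practice ("Patients will be excluded if they are not a patient at one of the 67 primary care practices"), age, visits and portal use ("have used the portal at least once within 12 months").

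On exposure, the protocol's arm table says of each text arm: "Participants in this arm will receive up to 3 R/R messages by text". The portal arms are messaged through the portal, and the control arm gets no reminder message. Reminders continue "until record of vaccine receipt appears in the patient EHR".

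On adjustment, the SAP says: "Models will adjust for patient characteristics, including age, sex, race/ethnicity, primary language, primary insurer, and prior year vaccination status".

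Neither document states an as-randomised analysis, or a sensitivity analysis that keeps opt-outs.

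**The concern.** A patient who opts out because of a study reminder text is responding to the assigned intervention. Portal and control patients get no such text and cannot respond in that way. Removing these patients conditions on an event after randomisation in one arm only, so the remaining text patients are no longer comparable with the other arms.

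The direction is not known in advance. If opt-outs are less inclined to be vaccinated, removing them raises the text arm's rate with no true effect, which is the direction the SAP hypothesises. If they are mainly people vaccinated elsewhere whose record has not yet reached the EHR and who are still being reminded, the bias runs against text.

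At stake is the first hypothesis in the SAP, that text does better than portal and than no reminder. The exclusion is not needed to obtain outcomes: vaccination status comes from the EHR, external sources and claims, whether or not the patient accepts texts.

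**Working it through.** **Nothing to reproduce.** The documents give no sample size, vaccination rate or opt-out rate. The only documented input is the 0.017 significance level; sidedness is not stated, and two-sided is assumed, so the critical value is 2.387. Everything else below is assumed for illustration: no true effect, p = 0.60 in every arm, n = 10,000 per arm, and no practice clustering.

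**Step 1: unadjusted.** Let f be the share of the text arm excluded beyond any exclusion common to all arms, and gap the amount by which opt-outs' vaccination rate falls below the average.

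- Spurious difference: d = f × gap / (1 − f). For f = 0.05 and gap = 0.10: 0.005 / 0.95 = 0.0053.
- SE = √[p₁(1 − p₁)/(n(1 − f)) + 0.6 × 0.4/n], with p₁ = 0.6 + d. Here SE = 0.0070.
- False-positive rate = P(|Z| > 2.387), where Z has mean d/SE = 0.75 and unit variance. Result: 5.2%.

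| Opt-out share | Gap (points) | Spurious difference (points) | False-positive rate |
|---|---|---|---|
| 5% | 0 | 0 | 1.7% |
| 5% | 5 | +0.26 | 2.5% |
| 5% | 10 | +0.53 | 5.2% |
| 5% | 20 | +1.05 | 18.9% |
| 1% | 10 | +0.10 | 1.8% |

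A reversed 10-point gap at 5% opt-out gives −0.53 points.

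**Step 2: adjusted for prior-year vaccination.** Further assumptions: 60% were vaccinated last year, and 80% of those and 30% of the rest are vaccinated this year (0.6 × 0.8 + 0.4 × 0.3 = 0.60). A share s of the gap arises because fewer opt-outs were vaccinated last year: their proportion is 0.6 − gap × s / 0.5. The rest, gap × (1 − s), is a shortfall within both strata. Whole-arm rates stay at 80% and 30%, so there is no true effect.

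Worked case: f = 0.05, gap = 0.10, s = 0.5.

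- There are 500 opt-outs, of whom 0.6 − 0.1 = 50% were vaccinated last year: 250 in each stratum, vaccinating at 75% and 25%.
- Left in the text arm, vaccinated last year: (4,800 − 187.5)/5,750 = 80.2%.
- Left in the text arm, not vaccinated last year: (1,200 − 62.5)/3,750 = 30.3%.
- A log-binomial model with arm and prior-year status, fitted to these expected counts against a comparator at 80% and 30%, gives RR 1.003 with SE(log RR) 0.0089, and a false-positive rate of 2.5%.

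All cases at 5% opt-out:

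| Share of gap explained | 10-point gap: RR, rate | 20-point gap: RR, rate |
|---|---|---|
| None | 1.007, 5.9% | 1.015, 23.0% |
| Half | 1.003, 2.5% | 1.006, 4.3% |
| Three quarters | 1.002, 1.9% | 1.003, 2.2% |
| All | 1.000, 1.7% | 1.000, 1.7% |

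With half the gap explained, 2% opt-out gives 1.8% (10 points) and 2.1% (20 points); 1% opt-out gives 1.7% and 1.8%.

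**Step 3: sensitivity to arm size.** The bias does not shrink with n, but the standard error does. With a 50% base rate, 5% opt-out and opt-outs vaccinating half as often as average, unadjusted at 0.05/3, the apparent RR is (1 − 0.05 × 0.5)/(1 − 0.05) = 1.026. The false-positive rate is about 14% at 5,000 per arm, 58% at 20,000 and 96% at 50,000. This is a deliberately large gap.

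**Step 4: under the proposed rule.** If all randomised patients are kept, or only opt-outs recorded before randomisation are removed alike in every arm, the null RR is 1.000 and the error rate stays at about 1.7%.

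**The case against.** The sentence names no arm, so read literally it covers portal and control patients too. The paragraph's other two exclusions look like definitions of the population. Its reference to practices sending reminders by text suggests that an opt-out flag could exist for patients in every arm. If the rule means that flag as it stood before randomisation, there is no bias.

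That reading is plausible, but the SAP does not state it. Naming no arm does not help if later opt-outs count, because opt-outs prompted by study reminder texts occur only in the text arms. Both limits, timing and equal application, are needed.

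The second argument is size: every rate is assumed, the model adjusts for prior-year vaccination and other characteristics, and at 1–2% opt-out with half the gap explained the error rate is at most 2.1%. This stands. The larger figures need several percent opting out and a gap that the covariates leave unexplained.

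Third, the SAP calls an indicator for portal-based reminders or prompts its main explanatory variable, and portal v. none is not directly affected. That limits the reach of the problem, but both text contrasts remain stated primary hypotheses.

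Finally, the protocol also plans this: "We will assess intervention effects for the included population, and also for the entire practice". The reason it gives is portal penetration, so it does not settle who counts as an opt-out.

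**Conclusion.** The concern holds and should be fixed. A rule that decides who enters the primary comparison can be followed as written and still break the randomisation for text v. portal and text v. none. It can also be read so that no bias arises, and two analysts could build different analysis sets from it.

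Confidence is high that the rule permits bias. The size and direction are unknown: they depend on the opt-out rate, on how opt-outs' vaccination differs from average, and on how much of that difference the covariates explain, none of which the documents give. The bias may be negligible.

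**What to change.** Replace the opt-out sentence in the SAP with:

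> Patients with a text opt-out recorded before randomisation are excluded from all arms by the same rule. All other randomised index patients are analysed in the arm to which they were randomised, including those who opt out of texts after randomisation. Excluding post-randomisation opt-outs is a labelled sensitivity analysis, with counts reported by arm.

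If no baseline opt-out exclusion is wanted, delete the first sentence and the word *other*. Either choice of population is legitimate.

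Three smaller points belong with it:

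- State that non-portal users are those who fail the protocol's portal criterion at baseline, not those who stop using the portal later.
- Keep the sentence on practices without text pre-appointment reminders, for the pre-appointment analysis only, and word it as an exception to the rule above.
- Say that the same opt-out rule applies to the household patients in the secondary measure.

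**Cost.** SAP wording and one sensitivity analysis, with no new outcome data. The baseline version needs the date of each opt-out, and the documents do not say whether it is stored; the version without a baseline exclusion does not need it for the primary analysis. Keeping opt-outs dilutes the text effect: if 5% opt out and gain nothing (assumed), a 2.0-point effect is estimated as 2.0 × 0.95 = 1.9 points; at an assumed 20%, 2.0 × 0.80 = 1.6 points.
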